1. PROTOCOL SUMMARY

1.1 Synopsis			
Title:	The Jewel IDE Study: A Clinical Evaluation of the Jewel P-WCD in Subjects at High Risk for Sudden Cardiac Arrest. ("JEWEL")		
Study Description:	Multi-center, prospective, single arm study of the Jewel Patch-Wearable Cardioverter Defibrillator (P-WCD) System in patients at high risk for Sudden Cardiac Arrest.		
Objective:	To demonstrate the safety and clinical effectiveness of the Jewel P-WCD.		
Endpoints:	Primary Effectiveness Endpoint: To demonstrate an observed inappropriate shock rate of no more than 2.0 inappropriate shocks per 100 patient-months.		
	Primary Safety Endpoint: To demonstrate an observed rate of subjects experiencing a clinically significant cutaneous Adverse Device Effects (ADE) of <15%.		
	Secondary Endpoints:		
	 To observe successful conversion of at least one shockable rhythm with a salvo of up to five (5) shocks. 		
	• To observe a compliance rate of subjects wearing the Jewel of greater than 14.1 average hours per day during a prescription wear period.		
Study Population:	A total of 290 analyzable adult subjects in the United States at risk for sudden cardiac arrest who are not candidates for or who refuse an implanted defibrillator. Specifically, subjects:		
	 a. with a measured left ventricular ejection fraction (LVEF) less than or equal to 40% (as assessed within the last 30 days prior to enrollment) AND identified as presenting with a diagnosis of an acute myocardial infarction (AMI), ischemic cardiomyopathy (includes congestive heart failure NYHA Class I – III), non-ischemic cardiomyopathy, or myocarditis; 		
	OR		
	 who have a temporary or long-term contraindication to receiving an ICD, who have had an ICD removed, or who refuse an ICD. 		
	OR		
	 whose ICD implantation is delayed due to COVID-19 infection or exposure- related risks. 		
Sites, Geographies:	Subjects will be enrolled at up to 60 participating sites in the United States.		
Study Intervention:	Jewel Patch Wearable Cardioverter Defibrillator ("Jewel") System		
	The Jewel is a P-WCD applied directly to a patient's torso in an anterior-apical monitoring vector. The Jewel is worn continuously, 24-hours per day, for up to 8-days per Patch Unit, for the duration of the prescription period.		
Total Study Duration:	18 months		
Subject Participation Duration:	Individual subject participation will be determined by their Investigator but will not exceed 180 days.		

1.2 Schema

Screening

- Obtain Informed Consent
- Screen potential subjects by Inclusion and Exclusion Criteria
- Demographics, Medical History, COVID-19 status obtained and documented

Subject Training and Enrollment

- Subject receives Device Training and Placement Accessory Fitting
- Subject places initial Jewel under guidance (Subject is now considered enrolled)
- Subject returns home with the Jewel and an Adhesive Electrode Patch and Battery Unit ("Patch Unit"). NOTE: Element Science may contact the Subject to provide additional training related to the device, product support, and/or information related to the subject's participation in the study at later timepoints.

Prescription Period – as prescribed by Investigator

- Day 2 Phone Call: Follow-up by Element Science to assess any subject support needs.
- Exchange 1- Exchange 4 Follow Up: Office Visit, Telemedicine Visit, or Phone Call: (the first 4 times the subject removes a Jewel and replaces the Patch Unit) collect Patch Unit replacement information/compliance, assessment of patient status, determine if patient needs assistance, training, or supplies from Element Science, determine if new or changes to Adverse Events (AE), medical information, medications; subject completes experience questionnaire. Optional: photographs of device placement.
- Exchange 5 Follow Up through end of prescription period: Office Visit, Telemedicine Visit, or Phone Call: collect Patch Unit replacement information/compliance, assessment of patient status, determine if patient needs assistance, training, or supplies from Element Science, determine if new or changes to AE(s), medical information, medications.

End of Study Assessment (Visit / Phone Call) - within 14 days of device removal

- Adverse Event Review
- Exit Interview
- Study Exit

PR-2053 Rev. E

1.3 Schedule of Activities (SoA) by the Site

Procedures	Screening	Training & Enrollment (Day 0)	Exchange 1 – Exchange 4	Exchange 5 – end of prescription period	Study Exit Visit (end of prescription ± 14 days)
Informed consent	х				
Demographics	х				
Medical history	х				
Weight & measurements	х				
Eligibility review (IC/EC)	х				
Jewel training		х			
Placement Accessory fitting		х			
Apply device		х	х	х	
Photos of device after application		х	X (optional)		
QOL questionnaire		х			х
Wear experience questionnaire			Х		
Occurrence of any shocks/deferrals			х	Х	Х
Changes to medications, health status			x	х	х
Subject request(s) for assistance, training, or supplies			x	х	
Adverse Event evaluation			х	х	х
Exit Interview					х

2. INTRODUCTION

2.1 Background and Study Rationale

Sudden Cardiac Death (SCD) is sudden, unexpected death often caused by Sudden Cardiac Arrest (SCA), an abrupt loss of heart function with no sign of blood circulation, and is the leading cause of natural death in the US, resulting in about 325,000 adult deaths each year.(1) SCA is most often caused by abnormal heart rhythms called arrhythmias which prevent the heart from adequately pumping blood to the body. Ventricular Fibrillation (VF), which is an erratic, disorganized firing of impulses from the ventricles is the most common life-threatening arrhythmia. Ventricular Tachycardia (VT), in which the ventricles of the heart rapidly contract due to improper electrical activity, can also potentially be life threatening.

While the Implantable Cardioverter Defibrillator (ICD) is typically implanted for long-term prevention of SCA in high-risk populations, there are temporary periods of time when ICD implantation is commonly deferred. Examples include the initial 40 days after myocardial infarction (MI), the initial 90 days after percutaneous coronary intervention (PCI) or coronary artery bypass grafting (CABG), or after ICD explantation. The WCD has become a viable option to treat these temporary periods of elevated risk for SCA. Patients are typically prescribed to wear a WCD 24 hours a day, 7 days a week for 40 to 90 days or longer until a medical decision is made on whether to implant an ICD.(2)

Time to defibrillation is the single most critical determinant of survival in SCA. Survival rates after VF decrease approximately seven to ten percent with every minute that defibrillation is delayed. (3) While rapid defibrillation with an Automatic External Defibrillator (AED) by nonmedical personnel can improve survival after out-of-hospital cardiac arrest, the time period between arrest and successful resuscitation must be short and the cardiac arrest must be witnessed. The development of a wearable cardioverter defibrillator has provided a new therapy option for patients who are at high risk of SCA, and may require a defibrillation shock without the assistance from a bystander.

The Jewel Patch Wearable Cardioverter Defibrillator is an automatic external cardioverter defibrillator that monitors patients at risk for SCA and provides a therapeutic shock if needed. It is intended to be worn at home or in hospital during temporary periods of time when ICD implantation is commonly deferred.

To date, only one manufacturer has a commercial product approved as a wearable automated external defibrillator. The ZOLL LifeVest WCD is currently available in the United States, Europe, Australia, Israel, Japan, and Singapore.

The clinical efficacy of external defibrillation shock waveforms used in the ZOLL LifeVest WCD and other AEDs has been well studied in the controlled environment of the electrophysiology (EP) lab. For example, with the replacement of monophasic damped sine waveforms with lower energy biphasic truncated exponential waveforms, clinical efficacy was compared by measuring first shock success rate in patients undergoing electrophysiologic testing. (3) With the ZOLL LifeVest WCD, clinical efficacy was also evaluated as part of a routine EP procedure in which ten (10) patients were induced into VF and the LifeVest was used to deliver a single defibrillation shock. (4) In this study, special WCD units were used that were manually charged and discharged by the physician to terminate the VF episode in a relatively short time period (mean duration of 32 seconds per episode).

The Jewel delivers a salvo of up to 5 shocks (150, 162, 162, 162, 162 joules) using a biphasic truncated exponential waveform that is adjusted based on the transthoracic impedance of the patient . In this clinical study, the objective is to demonstrate the safety of the Jewel and to collect efficacy data on termination of potentially lethal arrhythmias, such as life-threatening VT or VF.

2.2 Risk/Benefit Assessment

2.2.1 Known Potential Risks

Potential risks include many risks that exist in the patient population being studied (i.e., those at risk for sudden cardiac death). These risks vary in frequency and severity, and include:

- acceleration or induction of atrial or ventricular arrhythmias,
- angina,
- bradycardia,
- death,
- discomfort/pain,
- dizziness,
- fluid accumulation,
- heart block,
- heart failure,
- myocardial infarction,
- myocardial necrosis,
- myocardial trauma,

- non-elective intubation,
- reduced cardiac function,
- shortness of breath,
- stroke,
- syncope,
- tachyarrhythmias, including early, recurrent atrial fibrillation,
- thrombus,
- thromboemboli,
- valve damage,
- vasovagal response, and
- worsening heart failure.

Additional risks from P-WCDs and WCDs, including Jewel, vary in frequency and severity and include:

- Allergic contact dermatitis
- Annoyance
- Arrhythmia, supraventricular
- Asystole
- Bradycardia
- Brain injury
- Burns, thermal
- Cardiac Arrest
- Chest pain
- Death
- Discomfort, distress
- ECG changes
- Electric shock
- Hearing Loss
- Infection, systemic and/or topical
- Injury
- Irritation

- Itching
- Misdiagnosis
- Myocardial Trauma
- Overstimulation
- Pain
- Rash
- Shock, Anaphylactic
- Skin reactions, including but not limited to: discoloration, erosion, inflammation, irritation, tears
- Sudden cardiac death
- Syncope
 - Tachycardia
- Urticaria
- Ventricular fibrillation
- Ventricular tachycardia

Of note, the occurrence of inappropriate shocks, which is one of the known risks of using the Jewel and participating in this study, is the primary endpoint of the study.

2.2.2 Known Potential Benefits

The Jewel is an investigational device so it is possible that the subject may not receive any benefit from participating in the study. Subjects taking part in this study are at risk for SCA and are not otherwise candidates for, or refuse an ICD, so participating in the study and using the Jewel may have the potential to convert a life-threatening cardiac rhythm and prevent SCA in this at-risk population. The results of this study may help other people to gain access to the Jewel, which may result in the prevention of SCD.

2.2.3 Assessment of Potential Risks and Benefits

The Jewel has been developed and tested thoroughly to meet the electrical safety standards published by the International Electrotechnical Commission (IEC). The device is battery powered and operates at low levels of electrical current, except when delivering a defibrillation shock. The electrodes are attached to sticky, adhesive pads, which consist of materials that are widely used in commercially available medical adhesives. The patient population being evaluated is at risk for SCA, and the device being tested has the potential to convert life threatening rhythms in this population who would otherwise be dependent on bystanders and emergency medical personnel for administration of a life-saving therapy in a timely fashion. The results of Element Science's simulated human use and preclinical testing, combined with the risk analysis of the Jewel System, indicate that the risk-to-benefit profile of the Jewel is favorable for the patient. With a better patient experience, the Jewel is anticipated to have significantly better compliance, and therefore has potentially greater effectiveness than the current standard WCD, with an equivalent safety profile to the standard WCD.

3. OBJECTIVES AND ENDPOINTS

3.1 Objective

The objective of this study is to demonstrate the safety and clinical effectiveness of the Jewel P-WCD.

3.2 Endpoints

3.2.1 Primary Effectiveness Endpoint

To demonstrate an observed inappropriate shock rate of no more than 2.0 inappropriate shocks per 100 patient-months using a one-sided upper 97% confidence interval and >83% power at the interim analysis; and a 98% confidence interval and >98% power for the final analysis.

An inappropriate shock is defined as a shock delivered during a period where the study subject is not experiencing life threatening VT or VF. Only first inappropriate shocks will contribute the analysis of this endpoint. All inappropriate shocks will be reviewed and adjudicated by a Clinical Events Committee (CEC) and reported throughout the prescription period.

3.2.2 Primary Safety Endpoint

The primary safety endpoint is to observe a rate of subjects experiencing a clinically significant cutaneous Adverse Device Effects of <15%.

For the purpose of endpoint calculation, a cutaneous ADE will be considered clinically significant if it causes the subject to be permanently withdrawn from the trial by the Investigator.

All Adverse Device Effects and device-related Serious Adverse Events (SAE) will be tabulated and presented along with duration and severity. The proportion of subjects experiencing an ADE or SAE will also be presented. All device-related events will be reviewed by the Data Safety Monitoring Board (DSMB).

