4. STUDY DESIGN

4.1 Overall Design

This study is a multi-center, prospective, single-arm evaluation of the Jewel P-WCD in adult subjects at risk for sudden cardiac arrest, who are not candidates for or who refuse an implanted cardioverter defibrillator. The study will include up to sixty (60) sites in the United States. This design incorporates one interim analysis at 179 analyzable subjects and one final analysis at 290 analyzable subjects.

There is another analysis point once 100 subjects have completed their prescription wear time, which will be performed to support application for CE mark.

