7. STUDY DISCONTINUATION AND SUBJECT WITHDRAWAL

7.1 Discontinuation of Study Intervention

Subjects may remove the Jewel if required for situational circumstances as listed in the Patient Guide. Examples include but are not limited to: undergoing a medical procedure (for example, MRI, CT, or with the use of diathermy), or submerging of the body. Subjects will be counseled that Jewel removal for these reasons should be done as infrequently as possible, and only as absolutely required. These situational circumstances do not constitute discontinuation or withdrawal.

Subjects may discontinue use of the Jewel, either temporarily or permanently, if advised to do so by the Investigator. In cases where a subject discontinues use of the Jewel on their own (that is, without instruction from the Investigator), a protocol deviation should be filed. Discontinuation based on Investigator orders does not constitute a protocol deviation.

If the discontinuation is temporary and does not meet non-compliance criteria for study discontinuation, the subject may continue in the study through the duration of the prescription period, restarting use of the Jewel either independently or when advised by the Investigator. Any new clinically relevant finding that causes temporary Jewel discontinuation will be reported as an Adverse Event.

If the discontinuation is to be permanent, the subject will be withdrawn from the study. In the case of withdrawal, best efforts should be made to collect the Jewel and all used or unused Patch Units and to complete the Study Exit Visit CRF.

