7.2 Subject Withdrawal from Study

Subjects are free to withdraw from study participation at any time upon request. An Investigator may withdraw a subject from the study at their discretion. Possible reasons for study withdrawal include, but are not limited to:

- Pregnancy
- Significant study non-compliance
- Significant wear non-compliance: discontinuation of device wear for longer than eight (8) days that is not related to Investigator direction or situational circumstances.
- Any AE or other medical condition or situation occurring such that continued participation in the study would not be in the best interest of the subject.
- Disease progression which requires discontinuation of the study device.
- If the subject meets an exclusion criterion (either newly developed or not previously recognized) that precludes further study participation.

Reasons for subject withdrawal from the study will be recorded on the appropriate CRF. Subjects who sign the informed consent form but are not enrolled may be replaced. Subjects who sign the informed consent form, are enrolled, but who subsequently are withdrawn from the study will not be replaced.

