9.4.4 Planned Interim Analyses

A single interim analysis will be performed after 179 or more subjects have completed their prescription wear time. This analysis will be used to stop the trial early for both safety and effectiveness. The Type I error rate for this analysis will be set to 0.03.

There is another planned analysis once 100 subjects have completed their prescription wear time, which will be performed to support application for CE mark. The data will be summarized descriptively and no formal hypothesis testing will be done at this point, so no adjustment for the Type I error rate is necessary. The results of the 100 subject interim analysis will not be used to terminate the IDE trial prior to completion of enrollment and subject follow up.

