3.2. Per Protocol Population

A per-protocol analysis population will be defined as those subjects that are part of the Primary Analysis Population, have worn the Jewel on average for at least 14.1 hours a day, and are without major protocol deviations which may affect the primary safety or effectiveness endpoint measurements. Analyses on the safety and effectiveness endpoints will be repeated on this population.

3.3.Safety Analysis Population

The safety analysis population will consist of all subjects who remain enrolled for longer than 12 hours after the date and time the first Jewel applied to the subject's body transitions to Monitor Mode, regardless of analyzable wear time. For example, if a subject wore the Jewel and subsequently does not return the device or the device was damaged, this subject is still part of the safety analysis population and will be assessed for clinically significant cutaneous Adverse Device Effects.

4. Study Objectives

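### Primary safety test: skin-driven stops that the subject initiates are not counted, and the interim test by default counts subjects still in follow-up as non-events

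*Protocol*

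**What the plan says.** **Event.** Under Protocol 3.2.2, "a cutaneous ADE will be considered clinically significant if it causes the subject to be permanently withdrawn from the trial by the Investigator". SAP 5.3 sets the same condition. The test compares a one-sided exact 95% Clopper-Pearson upper bound with 15%.

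**Ways of stopping.** Protocol 7.2 gives two routes. One is the subject's own: "Subjects are free to withdraw from study participation at any time upon request". The other is withdrawal at the Investigator's discretion. The possible reasons it lists include an adverse event that makes continuing against the subject's interest, and wear non-compliance, described as "discontinuation of device wear for longer than eight (8) days that is not related to Investigator direction" (situational removals are also exempt). Protocol 7.1 adds a rule for self-initiated stops: "where a subject discontinues use of the Jewel on their own (that is, without instruction from the Investigator), a protocol deviation should be filed". It also says "If the discontinuation is to be permanent, the subject will be withdrawn from the study", without naming who is recorded as withdrawing the subject.

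**Population.** SAP 3.3 states: "The safety analysis population will consist of all subjects who remain enrolled for longer than 12 hours" after the first device enters Monitor Mode, whether or not their wear time is analyzable. SAP 3.2 repeats the safety analysis per protocol, with the same event definition.

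**Interim.** Protocol 4.1: "This design incorporates one interim analysis at 179 analyzable subjects and one final analysis at 290 analyzable subjects". Protocol 9.4.4: "A single interim analysis will be performed after 179 or more subjects have completed their prescription wear time". SAP 5.5 takes its method from SAP 5.1, the effectiveness model. It tests safety only if effectiveness is met and stops the trial only if both are met. It names no population for the safety test.

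**The concern.** **Numerator.** The safety question is how often the skin reaction ends use of the device. A subject who gives up because of it, without an Investigator's decision, has had that outcome but adds only to the denominator. Because Protocol 7.1 and 7.2 do not settle who is recorded as withdrawing a permanent discontinuer, two sites could code the same stop differently. The adverse-event, withdrawal-reason and deviation tables will show these cases, but nothing tests them against 15%.

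**Interim denominator.** SAP 5.1 lets subjects without an event at the time of analysis contribute. That suits a Poisson rate, where they bring only the wear time they have accrued. The safety endpoint is a proportion with no exposure term, so a subject two weeks into a three-month prescription counts as a complete non-event. This biases the interim rate down, in a test that is one of the two conditions for stopping early.

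**Working it through.** **1. The plan's own figures.** SAP section 8 gives no assumed event rate or power for safety, so there is no safety figure to reproduce. The effectiveness figures do reproduce when its simulation is repeated (20,000 studies): power 98.1% at 290 (stated: about 98%) and 83.8% at 179 (stated: above 83%).

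**2. Pass limits.** The upper bound for x events in n subjects is the 95th percentile of Beta(x+1, n−x). The test passes if this is below 15%.

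| n | last pass (bound) | first fail (bound) |
|---|---|---|
| 179 | 18 (14.55%) | 19 (15.19%) |
| 290 | 33 (14.92%) | 34 (15.30%) |
| 370 | 43 (14.73%) | 44 (15.03%) |

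**3. Uncounted stops, n = 290.** The verdict reverses once counted plus uncounted stops reach 34. With 25 counted, 34 − 25 = 9 uncounted are enough; with 15 counted, 34 − 15 = 19 are needed.

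If the true rate of skin-driven stops is 15% and a share s is self-initiated and uncounted, the pass probability is P(X ≤ 33), with X binomial(290, 0.15(1−s)). The documents give no value for s, so this range is an assumption.

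| s | 0 | 10% | 20% | 30% | 50% |
|---|---|---|---|---|---|
| pass | 4.6% | 17% | 42% | 73% | 99% |

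Away from the limit the issue fades. With every stop counted, P(X ≤ 33) is 81% at a true 10% and 98% at a true 8%.

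**4. Dilution at the interim, simple case.** Take 179 fully followed subjects at a true 15%, plus 45 still wearing the device who have accrued half their risk (an assumption). The expected rate is (179 × 0.15 + 45 × 0.075)/224 = 30.225/224 = 13.5%. The limit is 24/224 and the pass probability is 12.9%. For the 179 alone it is P(X ≤ 18) = 3.5%.

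**5. Dilution at the interim, simulated.** Inputs from SAP section 8: wear time normal, mean 2.5 and SD 0.5 months. Assumptions: Poisson accrual of 20 or 30 a month; events spread evenly over wear, or front-loaded as Beta(1,4); trigger at 179 prescription completers or at 179 exits of any kind.

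At a true 15%, the SAP 3.3 set averages about 223–285 subjects, of whom 44–69 are still in follow-up. The mean estimated rate is 12.8–14.4%. The safety test passes about 13–22% of the time (even timing) or 7–9% (front-loaded). The first 179 enrolled, fully followed, pass about 3.5% of the time.

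**6. What a 179-subject cohort gives up.** At a true 10%, it passes 57% of the time and the SAP 3.3 set 76–94%. Part of that gap is sample size: with complete follow-up the exact pass probability is 70% at n = 223 and 79% at n = 285. The cohort also leaves out known events in later enrollees, on average about 3–14 at a true 15%.

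**The case against.** **Numerator.** Protocol and SAP agree on the definition, and an Investigator can withdraw a subject for a skin reaction under Protocol 7.2, so many such cases may be counted anyway. The rest remain visible in planned tables. Nothing in the documents places the rate near 15%, and the self-initiated shares used above are assumed. All of this stands. It limits the point to a sensitivity analysis and gives no reason to change the primary definition.

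**Interim set.** A reader might infer that the documents contradict each other, pointing both to 179 subjects and to everyone enrolled. They do not support that. SAP 3.3 is the only safety population defined, and it is not confined to the final analysis. The 179 analyzable subjects in Protocol 4.1 describe the size of the interim, and SAP 3.3 expressly sets analyzable wear aside. The 179/290 fraction in SAP 5.5 belongs to the spending function for the effectiveness bounds. With one defined population, a fear that the set would be chosen after seeing the data is weak. What remains is that this default population includes incomplete follow-up.

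**Remedy.** A cohort limited by enrolment order ignores known events in later enrollees and loses precision. That is a fair criticism, and it is why the full SAP 3.3 result should be shown beside it.

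**Conclusion.** Both parts hold as improvements to consider; neither is an error in the plan.

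The first matters only near the limit: 33/290 passes and 34/290 fails, and at a true 8% the test passes 98% of the time whichever way stops are counted. Its size depends on a self-initiated share that the documents do not give.

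The second is a downward bias from applying SAP 3.3 at the interim. At a true 15% the safety test passes about 13–22% of the time with even event timing, or 7–9% front-loaded, against a nominal 5%. This rests on assumed accrual and event timing. A reader might take these figures as the chance of wrongly stopping the trial. They are not: safety is tested only after effectiveness has passed, and both must be met to stop.

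**What to change.** **SAP 5.3.** Keep the primary definition. Prespecify a sensitivity analysis that counts every permanent stop whose recorded cause is a device-related cutaneous ADE, whoever initiated it and including stops filed as wear non-compliance. Use the same one-sided 95% Clopper-Pearson bound against 15%. Reconcile Protocol 7.1 and 7.2 with 3.2.2 on who is recorded as withdrawing a permanent discontinuer. The cost is wording only, because withdrawal reason, relatedness and self-initiated discontinuation are already recorded.

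**SAP 5.5.** Base the interim safety test on a cohort fixed by enrolment order, for example the first 179 in the SAP 3.3 population, tested once each member has ended prescription or withdrawn. Report beside it the result for all SAP 3.3 subjects at the data cut, so that known events in later enrollees are seen before any decision to stop. Do not define the cohort by finished-or-exited status: subjects with events exit early, and at a true 15% that set estimates about 16–19%.

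The costs of the second change are:
- a possible wait (simulated mean 0–1 month, 95th percentile up to 1.5 months; longer if prescriptions run towards 180 days);
- a lower interim pass probability for an acceptable device (57% at a true 10%, 87% at a true 8%), in which case the trial goes on to the final analysis;
- events in later enrollees fall outside the formal test.
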